9.1 Treatment with CMVpp65 Specific T-cells

Eligible patients who consent to enter this trial and for whom CMV-pp65 CTLs are available, will receive 3 weekly infusions of CMV-pp65 CTLs. The T cells will be administered immediately after thawing. The final product is cryopreserved in a volume of 1-2 ml. This will be drawn up in a sterile syringe containing 30 ml of normosol for intravenous administration and administered by slow intravenous infusion ideally over approximately 5 minutes.

In this phase II trial, patients will be treated at doses of 1×10^6 CMVpp65-CTL/kg/dose/week for 3 weeks (+/- 20% variability of total dose). Patients will be observed for the following 3 weeks. Additional 3 week courses of CMVpp65-CTL may be administered if levels of CMV DNA in blood are still detectable despite disease stabilization or improvement.

If the planned dose of CMV peptide sensitized T-cells is not achieved, but the cells generated exhibit required levels of CMV specific cytotoxic activity and meet all other release criteria, the T-cell product may be administered at a lower dose level.

In certain cases, in order to avoid refreezing of the final product to achieve a specific dose level, which may affect viability, variability of each dose may exceed +/-20%. In such cases, care will be given to ensure that the total combined volume of the 3 doses does not exceed the planned dose.

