10.0 EVALUATION DURING TREATMENT/INTERVENTION

The timing of evaluations below is approximate. The schedule of tests described should be adhered to whenever possible. However, in certain situations, particularly late after treatment, circumstances may preclude assessments at the times specified, at which point they may be held at the discretion of the treating physician:

- Patients will be evaluated clinically by vital signs pre-infusion, post, and at approximately 1, 2, 3, and 4 following initiation of each infusion of CMV-specific T-cells
- The patient should be followed weekly for the first 8 weeks post-initial infusion with CMV-specific T-cells, then monthly until 6 months post initial infusion. Patients will receive interim history, review of systems, and physical exam (including GvHD evaluations) on the day of infusions, and on days 1, 8 and 15 whenever possible.
- Patients should be monitored by CBC and comprehensive metabolic panels weekly for the first 8 weeks post-initial infusion with CMV-specific T-cells, then approximately monthly until 6 months post initial infusion.
- Tests quantitating CMV viremia by CMV DNA copies per milliliter of blood should be obtained weekly for the first 8 weeks post-initial infusion with CMV-specific T-cells, then approximately monthly until 6 months post initial infusion
- Quantifications of T cells generating IFNy in response to pooled CMV pentadecapeptides or T cells specific for single pentadecapeptides known to be contained in the T cells infused should be measured weekly for the first 8 weeks post-initial infusion with CMV-specific T-cells, then monthly until 6 months post initial infusion. If the T cells infused are known to contain T cells that can bind specific CMV peptide/HLA tetramers, these T cells will also be quantitated.

- When possible, pre-initial infusion and at week 4 and month 6 post initial infusion, if >1% of the circulating T cells are found to be reactive against specific epitopes by either assay, these CMV-pp65-reactive T cells will, if possible, be characterized as to their T cell receptor V β repertoires, to determine whether and to what degree, the T cells expanding *in vivo* resemble (and, therefore, are likely to be derived from) the CMV-specific T cells infused at the time of adoptive transfer
- If there are clinical indications, research samples may be collected testing for cytokines.

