¹ GVHD evaluations to be performed weekly until Week 8 and a consensus at Day 100

² If patient is given additional cycles of CMV specific T-cells, calendar will restart from Day 0. Doses are given weekly and can be held at the discretion of the PI or in the case of severe toxicity related to infusion.

³ Prior to and at specific intervals following infusion of CMVpp65-CTL, patients will be monitored for levels of CMVpp65-CTL in the blood as measured by quantitation of CTL precursor frequencies, CMV pp65-specific IFNy+ T-cells (35), or epitope specific-T-cells binding HLA-peptide tetramers and their V β usage (36). The third party T-cells will also be monitored by analysis of CMVpp65 IFNy+ T-cells as to their genetic origin.

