12.0 CRITERIA FOR THERAPEUTIC RESPONSE/OUTCOME ASSESSMENT

The primary endpoint of this study is to assess whether the infusion of the CMVpp65-CTLs has therapeutic activity in curing CMV infections in recipients of HSCT. This study specifically will evaluate the therapeutic efficacy and persistence after infusion of CMVpp65-CTLs derived from the HSCT transplant donor for the treatment of CMV infections. The second clinical end point of this study is the evaluation of GvHD induction after infusion of donor derived CMVpp65-CTLs. .

The responses of CMV infections will be clinically monitored as detailed under section 10. Responses to adoptively transferred T-cells are usually not observed until the T-cells have had time to expand within the transplant recipient, a period of at least 3 days, and as many as 18-21 days after the T-cell infusion. Accordingly, initial patient responses will be scored at weekly intervals, from day 7-day 21 post the initial infusion. Final responses will be captured in CRDB and scored between days 28-42 post the final infusion. Outcome responses will be captured post-first cycle and post final-cycle of infusions of CMV specific T cells. Best response observed in the full course of treatment will also be recorded as a distinct entity.

Clinical responses will be considered complete if all manifestations of CMV disease have resolved and/or the patient no longer has detectable CMV DNA by PCR.

A partial response will be defined as a $2 \times \log_{10}$ reduction in the level of CMV DNA detected in the patients blood and/or improvement in clinical parameters of CMV infection such that the patient is symptom-free.

Stable disease will be defined as no change in the clinic severity of disease in any organ.

Progressive disease will be defined as disease progression by clinical and radiologic parameters, ascribable to CMV infection in any affected organ, with unchanged or increased levels of CMV DNA.

Graft versus Host Disease initially developing after 10 days post T-cell infusion will be considered to be potentially ascribable to the T-cell infusion. Graft versus Host Disease will be diagnosed and clinically graded using the standard criteria of the IBMTR/NMDP Consensus Panel. Whenever, possible, the diagnosis will be confirmed by biopsy of skin or other involved organ, using the pathological criteria of Woodruff et al. Patients with preexisting GvHD of grade 1 severity not requiring

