14.0 BIOSTATISTICS

A phase 2 trial design will be applied to determine the efficacy and safety of CMV specific T cells for the treatment of marrow transplant patients with CMV. The endpoint of this study is complete response, defined as the clearance of the CMV infection 3-7 weeks following completion of the last cycle of CMV CTLs. The evaluation of treatment efficacy will be assessed for patients receiving CMV specific T cells from their transplant donor. It is anticipated that accrual will be completed within 3 years.

A two-stage design with a maximum of 39 patients will be employed. The study design discriminates between population response rates of 0.50 and 0.70. In the first stage, 23 patients will be enrolled in the study. If 11 or fewer complete responses (CRs) are observed, then the trial will be stopped. If at least 12 complete responses are observed, then 16 additional patients will be accrued. At the conclusion of the trial, if 23 or fewer CRs are observed, we will conclude that the treatment is not sufficiently active. This design has power 0.90 for a population CR rate equal to 0.70 using a one-sided test with type 1 error equal to 0.10.

The probability of a complete response and the proportion of patients requiring ganciclovir or foscarnet will be computed.

Following approval of Amendment 22, additional accrual on study is anticipated to be 2-3 patients per year, for an additional 3 years, for a target accrual of approximately 7 additional patients. As the accrual will be lower than the originally targeted accrual number, there will be no hypothesis test for efficacy analysis and the efficacy analysis is to estimate the complete response (CR) rate with its 80% confidence interval. For example, with 9 CR observed among a total of 15 subjects, the estimate of CR rate is 60% with the 80% Clopper-Pearson exact confidence interval of (40.4%, 77.4%).

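### Section 12 lets either undetectable CMV DNA or resolved CMV disease count alone as complete response, and Sections 12 and 14 score that response over different windows

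*Combined protocol and SAP*

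**What the plan says.** **Definition.** Section 12.0 scores a response as "complete if all manifestations of CMV disease have resolved and/or the patient no longer has detectable CMV DNA by PCR". Partial response (PR) in the same section needs a 2 log10 fall in blood CMV DNA and/or "improvement in clinical parameters of CMV infection such that the patient is symptom-free". Section 14.0 gives the endpoint as "complete response, defined as the clearance of the CMV infection 3-7 weeks following completion of the last cycle of CMV CTLs", without saying whether clearance is virological, clinical or both. No section assigns a limb to a type of patient or says which category prevails when two are met. Section 6.2.1, item 1, admits patients with documented CMV disease, with microbiological evidence such as viremia, or with both.

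**Timing.** Section 12.0 states: "Final responses will be captured in CRDB and scored between days 28-42 post the final infusion". It adds: "Outcome responses will be captured post-first cycle and post final-cycle of infusions of CMV specific T cells". Section 14.0 counts 3 to 7 weeks from the end of the last cycle but does not tie that end to a day. Section 9.1 sets three weekly infusions and then says: "Patients will be observed for the following 3 weeks".

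**Testing.** Section 10.0 says: "Tests quantitating CMV viremia by CMV DNA copies per milliliter of blood should be obtained weekly for the first 8 weeks post-initial infusion", and roughly monthly after that to month 6. Footnote 2 to the schedule says: "Doses are given weekly and can be held at the discretion of the PI".

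**Analysis.** Under Section 14.0, Amendment 22 drops the hypothesis test. Efficacy is now the estimated CR rate with an 80% Clopper-Pearson interval, illustrated by 9 CRs in 15 patients: 60% (40.4%, 77.4%).

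**The concern.** Two assessors can follow Section 12 and score the same patient differently. On the literal text, a patient with persisting CMV pneumonia and a negative PCR is a CR. So is a patient whose manifestations have all gone but whose DNA is still detectable, and that patient fits the PR text as well. Because the CR rate is now the whole efficacy result, the definition of CR determines what the trial reports. The confidence interval reflects sampling error only and does not cover this ambiguity.

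The timing adds a second, smaller source of disagreement. Two sections give windows of different width for the same endpoint, and one of them has no stated starting day.

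**Working it through.** **1. The protocol's own figure.** For x responders in n, the 80% Clopper-Pearson limits are the 10th percentile of Beta(x, n-x+1) and the 90th percentile of Beta(x+1, n-x). With x = 9 and n = 15 these are 40.35% and 77.44%, which reproduces Section 14's (40.4%, 77.4%).

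**2. Which patients are affected.** For a patient with both disease and viremia:

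| Manifestations | CMV DNA | Literal rule | Every applicable limb required |
|---|---|---|---|
| resolved | undetectable | CR | CR |
| resolved | detectable | CR (PR text also met) | not CR |
| persisting | undetectable | CR | not CR |
| persisting | detectable | not CR | not CR |

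The literal count minus the strict count is the number of such patients who met exactly one limb. It cannot be negative, so the literal rule can only raise the rate or leave it unchanged. A patient to whom only one limb ever applied scores the same under both rules, provided a limb that never applied is not treated as met.

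**3. Size, in the protocol's example.** The documents give no split of patients by limb. Assume that 0, 1 or 2 of the 9 CRs met only one of two applicable limbs:

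| Reclassified | CR rate | 80% interval |
|---|---|---|
| 0 | 9/15 = 60.0% | 40.4% to 77.4% |
| 1 | 8/15 = 53.3% | 34.2% to 71.8% |
| 2 | 7/15 = 46.7% | 28.2% to 65.8% |

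Each patient moves the rate by 1/15 = 6.7 points. The interval for 9/15 is 77.4 - 40.4 = 37.0 points wide.

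**4. The windows, in days after the final infusion.** Section 12 covers 28-42, which is 15 days. If the cycle ends at the last infusion, Section 14 covers 3 x 7 = 21 to 7 x 7 = 49, which is 29 days and contains all 15. If the three observation weeks belong to the cycle, Section 14 covers 21 + 21 = 42 to 49 + 21 = 70, and only day 42 is shared. The widths differ, so no anchor makes the two sections agree exactly.

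The text favours the first reading. Section 12 speaks of a cycle of infusions, Section 14 speaks of courses of cell infusions, and Section 9.1 calls a course three weeks long and places observation after it.

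**5. Scheduled weekly PCRs in each window**, taking Section 14 as days 21-49 and counting study days from the first infusion of the last cycle:

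| Last dose | Section 12 | Section 14 |
|---|---|---|
| Day 14 (on schedule) | Days 42-56: weeks 6, 7, 8 | Days 35-63: weeks 5, 6, 7, 8 |
| Day 21 | Days 49-63: weeks 7, 8 | Days 42-70: weeks 6, 7, 8 |
| Day 28 | Days 56-70: week 8 | Days 49-77: weeks 7, 8 |
| Day 35 | Days 63-77: none | Days 56-84: week 8 |

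For an on-schedule patient scored on the last weekly PCR in the window, week 8 decides under both sections. On the less likely reading (days 42-70 after the last infusion, so study Days 56-84), week 8 is again in the window, and the Month 3 test would displace it only if drawn by Day 84.

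**The case against.** The best defence is that the intent is clear: the PCR limb is meant for patients with viremia only, and both limbs for patients with disease and viremia. Section 14's reference to clearing the infection leans that way. That may well be the intent, but neither section says it, and the literal text gives a different answer for the two middle rows of the table in step 2.

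It is also fair to say that no stated figure is wrong, that no accept-or-reject decision remains, and that one patient's shift is small beside a 37-point interval. All of that stands and limits the weight of the point.

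On timing the defence is stronger. A reader might infer that the two windows are almost disjoint, sharing a single day. The documents do not support that as the natural reading, because their wording points to a cycle that ends with dosing, and then one window lies inside the other. The mismatch matters mainly when dosing is delayed, when the week 8 PCR is missing, or when a rule other than the last PCR in the window is used.

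A reader might also infer that the type I error of the 23 + 16 patient design is inflated. Amendment 22 removed that test, so the consequence falls on the estimate only. Best response is recorded as a separate item and does not compete with the final CR.

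**Conclusion.** The point holds and should be fixed. The ambiguous limb rule is the main part and the window mismatch is secondary. Following Section 12 as written can count as CR a patient with active CMV disease or with detectable DNA, and it leaves CR and PR overlapping. Relative to requiring every applicable limb, any effect on the CR rate is upward. Its size is 6.7 points per affected patient in the protocol's 15-patient example; the 0 to 2 patients used above are an assumption.

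Two stronger conclusions do not follow. The documents do not show that the CR rate is in fact overstated, since the number of patients who had both limbs and met only one is not given and may be zero. Nor do they show that a viremia-only patient becomes a CR by default for having no manifestations: resolution presupposes something to resolve, and nothing in Section 12 says that an absent limb counts as met.

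**What to change.** Put the same wording in Sections 12 and 14:

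- **CR** means meeting every limb that applies to the patient: blood CMV DNA undetectable if the patient was viremic at entry or later, and all CMV manifestations resolved if disease was present at entry or arose later. State how a patient enrolled on virus in tissue or body fluid alone is scored, so that nobody is left without an applicable limb.
- **PR** applies only to patients who are not CR.
- **One window and one anchor**, for example days 28-42 after the final infusion actually given, with a statement of which PCR counts if several fall in it.
- **Missing PCR.** A patient for whom the PCR limb applies and who has no PCR in the window counts as not CR, and the number of such patients is reported. This does not apply to patients who were never viremic.
- **Sensitivity analysis.** Report the CR rate with either applicable limb sufficient. A limb that never applied does not count as met there.

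Fix the rule in writing before re-scoring, then apply it to all patients from data on file. Redefining CR after patients have been treated invites an outcome-driven choice; the prior written rule and the sensitivity analysis guard against that.

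The cost is wording in two sections and a re-score, with no new tests. The reported CR rate may be lower. Some patients may count as not CR only because of late dosing or missed tests: with days 28-42, a final infusion three weeks late leaves no scheduled weekly PCR in the window, whereas days 21-49 would keep week 8. That trade-off should be weighed when the single window is chosen.

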6.2 Subject Inclusion and Exclusion Criteria

6.2.1 Patient Inclusion Criteria

1. Each patient must satisfy at least one of the following criteria:

- a. The patient must have a clinically documented condition associated with CMV (e.g. interstitial pneumonia, hepatitis, retinitis, colitis)
Or
- b. The patient must have microbiological evidence of CMV viremia or tissue invasion as attested by viral culture, or detection of levels of CMV DNA in the blood or body fluids consistent with CMV infection.

2. Patient must also satisfy at least one of the following criteria:

- a. The patient's CMV infection is clinically progressing or CMV viremia is persistent or increasing (as evidenced by quantitation of CMV DNA in the blood) despite two weeks induction therapy with antiviral drugs.
Or
- b. The patient has developed CMV viremia as attested by viral culture, or detection of levels of CMV DNA in blood or body fluids while receiving prophylactic doses of antiviral drugs to prevent CMV infection post transplant.
Or
- c. The patient is unable to sustain treatment with antiviral drugs due to drug associated toxicities (e.g. myelosuppression [ANC < 1000/ μ l/ml without GCSF support] or nephrotoxicity [corrected creatinine clearance \leq 60 ml/min/1.73 m 2 or serum creatinine $>$ 2 mg/dl])

3. Patient has CMV specific T-cells from the donor of his/her HSCT available.

4. CMV infections are life threatening, and may involve multiple organ systems such as the lungs, liver, gastrointestinal tract, hematopoietic and central nervous systems. Antiviral drugs used for treatment may also compromise renal and hematopoietic function. Therefore, dysfunctions of these organs will not affect eligibility for this protocol.

5. Patients must meet the following clinical criteria to receive CMVpp65-CTL infusions

- a. Stable blood pressure and circulation, not requiring pressor support
- b. Evidence of adequate cardiac function as demonstrated by EKG and/or echocardiography.
- c. A life expectancy of at least 3 weeks, even if requiring artificial ventilation.
- d. There are no age restrictions

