13.0 CRITERIA FOR REMOVAL FROM STUDY

In accordance with the Declaration of Helsinki, ICH Good Clinical Practice Guidelines, and the US FDA Regulations, a patient has the right to withdraw from the study at any time for any reason without prejudice to his/her future medical care by the physician or at the institution. The Investigator also has the right to withdraw patients from the study (see below). Should a patient (or a patient's legally authorized representative) decide to withdraw, all efforts will be made to complete and report the observations as thoroughly as possible.

A complete final evaluation should be made at the time of the patient's withdrawal, the Study Status Outcome form in the case report form should be completed with an explanation of why the patient is withdrawing, and an attempt should be made to perform a follow-up evaluation.

Patients may be removed from study if one or more of the following events occur:

- Significant noncompliance on the part of the patient
- Refusal of the patient to continue treatment or observations
- Unacceptable toxicity (i.e.: grade 3-4 toxicity related to CMV CTL infusion). Removal for unacceptable toxicity does not necessarily preclude continued follow-up.
- Progressive disease that in the Investigator's opinion requires therapeutic intervention that would interfere with the interpretation of results from the study
- Decision by the Investigator that termination is in the patient's best medical interest
- Unrelated medical illness or complication
- Lost to follow-up.

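### Section 12 scores rising CMV DNA without organ disease as stable, and leaves organ progression with falling DNA either unclassified or open to PR or CR

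*Combined protocol and SAP*

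**What the plan says.** All references are to the combined protocol and SAP.

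- **Who enters.** Section 6.2.1, criterion 1, accepts a documented CMV condition (1a) or, as an alternative, 1b: "The patient must have microbiological evidence of CMV viremia or tissue invasion as attested by viral culture, or detection of levels of CMV DNA". A patient can enter with viremia and no organ disease. Criterion 2a then counts as failure of antiviral drugs that "CMV viremia is persistent or increasing (as evidenced by quantitation of CMV DNA in the blood) despite two weeks induction therapy".
- **Response categories (Section 12.0).** CR: "all manifestations of CMV disease have resolved and/or the patient no longer has detectable CMV DNA by PCR". PR: a 2 log10 "reduction in the level of CMV DNA detected in the patients blood and/or improvement in clinical parameters of CMV infection", to the point of having no symptoms. SD: "Stable disease will be defined as no change in the clinic severity of disease in any organ". PD: "disease progression by clinical and radiologic parameters, ascribable to CMV infection in any affected organ, with unchanged or increased levels of CMV DNA".
- **When they are recorded.** Weekly from day 7 to day 21 after the first infusion; finally at days 28-42 after the last infusion; after the first and the final cycle; and as best response (Section 12.0).
- **Where similar words recur.** Further courses "may be administered if levels of CMV DNA in blood are still detectable despite disease stabilization or improvement" (Section 9.1, and in the same terms in Section 4.3). Section 13.0 lists among its grounds for removal: "Progressive disease that in the Investigator's opinion requires therapeutic intervention that would interfere with the interpretation of results from the study".
- **Endpoint.** Section 14.0 names complete response as the endpoint. Since Amendment 22 the efficacy analysis estimates the CR rate with an 80% interval, without a hypothesis test.

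**The concern.** Persistent viremia is a named treatment target (Section 2.0, primary objective 1), and lowering viral load in the individual patient is secondary objective 1. CR and PR can each be reached through CMV DNA. PD cannot, and SD places no limit on DNA. The scale therefore registers virologic success but not virologic failure in patients who have viremia only. A rise that would have qualified a patient for the trial as a drug failure is called stable once the T-cells have been given.

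The second gap concerns organ disease. PD is available only if blood DNA is unchanged or increased, so a patient whose organ disease worsens while DNA falls cannot be scored as progressing. Section 11.0 (item 2, specific immune reactions) expects that T-cells may transiently worsen an infected organ, so this combination is foreseeable.

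What is at stake is the meaning of the SD and PD counts. As written, SD mixes patients who are truly stable with patients in virologic failure.

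**Working it through.** The plan gives no figure for this point. The check applies the four Section 12.0 definitions literally to each combination of organ status and change in CMV DNA from the pre-infusion value. The PR threshold is read as a 2 log10 (100-fold) fall.

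| Organ status | CMV DNA | Categories met |
|---|---|---|
| No organ disease, or no change | rise | SD |
| | unchanged | SD |
| | fall below 2 log10 | SD |
| | fall of 2 log10 or more, still detectable | PR (SD wording also met) |
| | undetectable | CR (SD wording also met) |
| Clinical and radiologic progression | rise | PD |
| | unchanged | PD |
| | fall below 2 log10 | none |
| | fall of 2 log10 or more, still detectable | PR allowed by and/or |
| | undetectable | CR allowed by and/or |

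1. *First row.* There is no affected organ, so PD fails. PR fails because DNA has not fallen and there were no symptoms to improve. SD is met because no organ has changed. This holds for a rise of any size.
2. *CR in the first row.* With no organ manifestations, the first limb of CR could be argued to be met trivially. If viremia itself counts as a manifestation, or if Section 14.0's requirement that the infection be cleared is used, rising DNA is not CR and SD is the only category left. That ambiguity is separate from this point.
3. *Against entry.* Criterion 2a calls increasing viremia after two weeks of induction therapy a failure. Section 12.0 has no matching on-study category, and no other section supplies one.
4. *Lower block.* PD is reached in only two of the five rows in which an organ is progressing.
5. *Effect on the planned estimate.* SD and PD are both non-CR, so moving a patient between them leaves the CR count unchanged. Section 14.0's example is reproduced: 9 CRs in 15 patients gives 9/15 = 60%, with an 80% Clopper-Pearson interval from the 0.10 quantile of Beta(9, 7) = 40.4% to the 0.90 quantile of Beta(10, 6) = 77.4%. Nothing here alters it.
6. *How many patients are exposed.* The viremia-only share is not stated. As an assumption, take 50-80% and the 15 patients of Section 14.0's example: 0.5 × 15 = 7.5 and 0.8 × 15 = 12, or about 8 to 12 patients. These are patients to whom the first block could apply, not patients who would be misclassified.

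**The case against.** The strongest reply is that no planned analysis uses SD or PD. The endpoint is CR, every failure is counted as non-CR, and Section 14.0 has no progression rate and no stopping rule based on PD. CMV DNA is measured weekly for 8 weeks and then monthly to 6 months (Section 10.0), and its trajectory is analysed separately (Section 14.0). The gap is thus in a label, and the underlying data are kept. This stands, and it limits the weight of the point.

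A reader might also infer four stronger things that the documents do not support:

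- *That a viremia-only patient can never be scored PD.* PD covers any affected organ, so new CMV organ disease with unchanged or rising DNA could qualify.
- *That failures and harms in general are recorded as stable.* Only rising or unchanged DNA without organ change gets that label. Worsening organ disease cannot be SD, because SD requires no change in any organ. Inflammatory worsening may also be captured as a toxicity or a serious adverse event (Sections 11.0 and 17).
- *That PD is impossible in retinitis or enteritis for want of imaging.* This needs the strictest reading of the link between clinical and radiologic. Section 12.0 refers to Section 10 for monitoring, which assigns eye examinations, stool measures and colonoscopy to those sites, so the applicable method is a fair reading. The wording should be made explicit.
- *That the label decides treatment or removal.* Sections 4.3, 9.1 and 13.0 are permissive and do not cite the Section 12.0 categories. Section 13.0 also lets the investigator act on other grounds.

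What survives is that the stated rule yields a wrong recorded category for a population the trial sets out to treat, and no category for a foreseeable clinical course.

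**Conclusion.** The point holds as a defect in the SD and PD definitions. A patient who entered on viremia alone and whose CMV DNA rises without organ disease is scored stable, against the sense of criterion 2a. Organ progression is unclassified when DNA falls by less than 2 log10, and may be called PR or CR when it falls further. The affected outputs are the weekly, post-first-cycle, post-final-cycle and best-response categories. The SD/PD split does not affect the CR rate or its 80% interval.

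The conclusion rests on reading Section 12.0 as written and does not depend on the assumed share of viremia-only entrants, which governs only how many patients are exposed. With a small sample and estimation in place of a test, each recorded category carries weight in the descriptive report, so the wording should be amended.

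**What to change.** Amend Section 12.0, for outcome scoring only:

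- **PD** is met by either (a) worsening of CMV disease in an organ, or new CMV organ disease, shown by the applicable method (clinical or radiologic), whatever the blood DNA; or (b) a confirmed rise in CMV DNA above the pre-infusion value. The sponsor sets the amount of the rise and the confirmation rule in advance, having regard to the lag of up to 18-21 days that Section 12.0 allows for a response.
- **SD** requires both no organ change and CMV DNA within the limits for neither PR nor PD.
- **Precedence.** State which category prevails when two are met. Limb (a) overlaps CR in one cell, worsening organ disease with undetectable DNA. Whether that is a CR under Section 14.0 should be settled in the same amendment, since it is the only place where this change could touch the CR count.

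Fix the threshold before re-scoring existing patients from the PCRs already collected, and report the category under the current wording beside the new one.

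Sections 4.3, 9.1 and 13.0 speak of stabilization or progressive disease without saying whether the Section 12.0 definitions apply. They must be reconciled with Section 12.0. No clinical rule is proposed here.

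The cost is amended wording and a re-scoring exercise. No new test is needed, because PCR is already scheduled weekly to week 8. The downside is that some patients now labelled SD become PD, and a patient scored PR while an organ worsened would also move.
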